10.4.3.3 For blind study

Protocol_DST and OSMS_oral feeding performance

For the blind study, all interventions are conducted with the screen in place. For the control group, the researcher spends time with the patient next to them while keeping the screen up at the same time as in the intervention group. The researcher inserts their hand into the incubator and spends 15 minutes without performing any interventions.

8. Study evaluation

8.1 Basic clinical factors

- Gestational age, birth physical measurements, sex, singleton/twin, delivery type, Apgar score, umbilical cord blood gas findings, birth place, pregnancy complications, use of antenatal steroids, presence of pathological chorioamnionitis
- Public insurance status (general insurance vs. social assistance), marital status, parents' education level, parents' age, parents' occupation
- Neonatal respiratory distress syndrome, confirmed sepsis, patent ductus arteriosus (treatment status), abnormal findings on brain ultrasound, necrotizing enterocolitis requiring medical treatment, apnea of prematurity (treatment status), timing of discontinuation of apnea medication, feeding intolerance (treatment status), neonatal rickets, bronchopulmonary dysplasia, duration of mechanical ventilation (invasive, non-invasive, supplemental oxygen)
- Age (postnatal days, postmenstrual age) and physical measurements, feeding volume, and respiratory support methods at the following time points:
 - * When the initial gavage feeding starts,
 - * When the intervention begins,
 - * When the feeding volume reaches 120 ml/kg/d,
 - * When the first oral feeding begins,
 - * When the oral feeding volume reaches 50% and 100% of 120 ml/kg/day,
 - * When all feeding transitions to oral feeding, regardless of feeding-related side effects,
 - * When full oral feeding is possible without any feeding-related side effects that require special treatment (end of intervention),
 - * When full oral feeding is possible without any feeding-related side effects.
- The day of birth weight recovery, duration of TPN, duration of gavage feeding, type of milk, period until resolution of feeding-related apnea, bradycardia, and oxygen saturation decrease after reaching full oral feeding.
- Total hospitalization period, age (in postnatal days, postmenstrual age) and physical measurements at discharge.
- Results of developmental assessment tests for long-term developmental evaluation in eligible patients for clinical purposes:
 - * Bayley Scales of Infant and Toddler Development, 3rd Edition (corrected age 18-24 months)

Protocol_DST and OSMS_oral feeding performance

(Indications: GA < 32 weeks or BW < 1500g)

* Korean version of the McArthur-Bates Communicative Development Inventory (at 36±2 months) (Indications: GA < 32 weeks)

* Korean Wechsler Preschool and Primary Scale of Intelligence, 4th Edition (K-WPPSI-IV) (from 4 years to less than 5 years of age) (Indications: GA < 29 weeks or BW < 1000g)

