Outcomes	
 1. Time from initiation of oral feeding to full oral feeding 2. Oral feeding performance 3. Neonatal Oral Motor Assessment Scale (NOMAS) 4. Bayley Scales of Infant and Toddler Development, Third Edition: CA 18-24months 5. Korean Version of MacArthur-Bates Communicative Development Inventories (K M-B CDI): postnatal age 36 ± 2 months 6. Korean-Wechsler Preschool and Primary Scale of Intelligence (K-WPPSI)-Fourth Edition: 4:0~4:11 years 7. Korean Developmental Screening Test for Infants (K-DST) : postnatal age 48 ± 3 months 8. Strengths and Difficulties Questionnaire (SDQ) : postnatal age 48 ± 3

Protocol_DST and OSMS_oral feeding performance

	months 9. Behavioral Pediatric Feeding Assessment Scale (BPFAS) : postnatal age 48 ± 3 months
Expected outcomes and potential impact	It is expected that the group receiving DST will show improved oral feeding abilities compared to the control group. Furthermore, the combination of OSMS with DST is anticipated to have a synergistic effect, further enhancing oral feeding skills. Additionally, it is expected that interventions during the neonatal period will have a lasting impact on long-term development and feeding behaviors.

Protocol_DST and OSMS_oral feeding performance

1. Title of the clinical trial

The effects of direct swallowing training and oral sensorimotor stimulation in preterm infants

2. Name and Address of the Clinical Trial Institution

Institution Name: Seoul National University Children's Hospital
Address: [name]

3. Study period

From IRB approval date in 2015 to December 30, 2025.

4. Objectives of study

We will observe whether the application of direct swallowing training (DST) and oral sensorimotor stimulation (OSMS) to preterm infants, preparing for the transition from gavage feeding to oral feeding, shortens the period of transition to full oral feeding and improves oral feeding ability. Additionally, we will evaluate the long-term impacts of oral feeding interventions in the neonatal intensive care unit (NICU) on development, feeding behaviors, and other related factors.

5. Study Design

single-center, prospective, open-label, controlled, randomized study

6. Study participants

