6.2 Target sample size and rationale for calculation

The primary objective of this study is to determine whether there is a difference in the time taken to reach full oral feeding, from the initiation of oral feeding, when DST and OSMS are applied to preterm infants preparing for the transition from gavage feeding to oral feeding.

To calculate the sample size required to achieve the research objective, the following assumptions are made:

Protocol_DST and OSMS_oral feeding performance

(1) Level of significance (α): 0.0167 (two-tailed test).

When comparing the control group with the DST group, the control group with the DST + OSMS group, and the DST group with the DST + OSMS group, there is an issue of multiple comparisons. To address this, Bonferroni correction is applied. The significance level used is $0.05/3 = 0.0167$.

(2) Group ratio: Control group : DST group : DST + OSMS group = 1 : 1 : 1.

(3) Type II error (β): 0.20, maintaining a test power of 80%.

(4) Primary outcome: Days from start to full oral feeding (SOF-FOF).

(5) The hypothesis of the study is as follows:

[Hypothesis 1]

Null hypothesis: There is no difference in SOF-FOF days between the control group and the DST group.

Alternative hypothesis: There is a difference in SOF-FOF days between the control group and the DST group.

[Hypothesis 2]

Null hypothesis: There is no difference in SOF-FOF days between the control group and the DST + OSMS group.

Alternative hypothesis: There is a difference in SOF-FOF days between the control group and the DST + OSMS group.

[Hypothesis 3]

Null hypothesis: There is no difference in SOF-FOF days between the DST group and the DST + OSMS group.

Alternative hypothesis: There is a difference in SOF-FOF days between the DST group and the DST + OSMS group.

(6) Sample size calculation method: The PASS program (Power Analysis and Sample Size software; <http://www.ncss.com>) will be used.

Based on existing research data (16, 18), the average SOF-FOF days for each group were assumed as follows: Control group 20.8 days, DST group 14.6 days, and DST + OSMS group 10.0 days. The pooled standard deviation was calculated to be 7.19. With a significance level of 1.67% and a two-tailed test, the required sample size for 80% power is 56 participants per group, for a total of 168 participants.

Protocol_DST and OSMS_oral feeding performance

Assuming a 10% dropout rate, the final sample size, accounting for dropouts, is 189 participants.

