8.4.2 Statistical Analysis Methods

- Statistical Software: SPSS for Windows (version 19.0)
- Continuous Variables: Mann-Whitney U test, One-way ANOVA
- Categorical Variables: Chi-square test, Fisher's exact test
- Evaluation of the Effect of Interventions on Primary and Secondary Outcomes:
 - Two-way analysis of variance
 - Repeated measures analysis of variance
 - Post-hoc analysis, if necessary
- Univariate/Multivariate Analysis: Binary and multiple logistic regression analysis
- Unless otherwise specified, all statistical tests will be conducted at a two-sided significance level of 0.05.

9. Drop out

<Criteria for Clinical Trial Dropout>

- When the guardian requests discontinuation of the clinical trial or withdraws consent for participation.
- When the participant experiences respiratory deterioration during the trial period, requiring the use of a respiratory device beyond nasal positive pressure ventilation.
- When the participant experiences gastrointestinal deterioration during the trial period, necessitating fasting for more than 48 hours.
- When a serious adverse event occurs.

10. References

- 1) American Academy of Pediatrics Committee on Fetus and Newborn. Hospital discharge of the high-risk neonate. *Pediatrics* 2008;122:1119-26.
- 2) Bragdon DB. A basis for the nursing management of feeding the premature infant. *JOGN Nurs* 1983;12(3 Suppl):51s-7s.
- 3) Gryboski JD. Suck and swallow in the premature infant. *Pediatrics* 1969;43:96-102.
- 6) Bingham PM. Deprivation and dysphagia in premature infants. *J Child Neurol* 2009;24:743-9.

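### No covariate-adjusted model is named for the continuous long-term scores, although birth size and parents' education are already recorded, so some precision is given up

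*Combined protocol and SAP*

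**What the plan says.** Section 4 makes later development a stated aim: "we will evaluate the long-term impacts of oral feeding interventions in the neonatal intensive care unit (NICU) on development, feeding behaviors, and other related factors". Section 8.3.2 lists six long-term instruments among the secondary outcomes.

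Section 8.1 records size at birth, gestational age, sex and insurance status, and on the family side "marital status, parents' education level, parents' age, parents' occupation". Section 7.2 stratifies the randomisation by gestational age and sex.

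In section 8.4.2, continuous variables are assigned the Mann-Whitney test and one-way ANOVA. Under "Evaluation of the Effect of Interventions on Primary and Secondary Outcomes" the section lists two-way ANOVA, repeated measures ANOVA and post-hoc tests where needed. The second factor of the two-way ANOVA is not named. The only multivariable regression listed is logistic, without covariates. No ANCOVA or linear regression appears, and no method is tied to any individual long-term score. Section 8.4.1 uses birth weight and gestational age to define subgroups only. Parents' education has no role in the analysis.

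Section 8.1 limits K-WPPSI-IV to children born before 29 weeks or weighing under 1000 g.

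**The concern.** Birth size and parents' education precede the intervention and can be expected to predict developmental and behavioural scores years later. A baseline variable that predicts the outcome, when put in the model, removes part of the residual variance and so shortens the interval for every arm contrast. The variables are already being collected, so leaving them out forgoes precision that costs almost nothing.

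The trial was sized on feeding days alone. No SD, effect size or power is given for any long-term score, so precision there is whatever 189 infants happen to provide, and less for K-WPPSI-IV. There is a second benefit to naming the model now: with six instruments and a long list of recorded background variables, an unspecified model leaves room to choose covariates after the results are seen.

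**Working it through.** **1. The plan's own figure.** Section 6.2 assumes "Control group 20.8 days, DST group 14.6 days, and DST + OSMS group 10.0 days" and states "The pooled standard deviation was calculated to be 7.19". Significance is 0.0167 two-sided and power 80%. The smallest contrast is 14.6 - 10.0 = 4.6 days.

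- Normal formula: n = 2 x [7.19 x (2.393 + 0.842) / 4.6]^2 = 51.1, so 52 per arm.
- Two-sample t-test (noncentral t): 53 per arm.
- Mann-Whitney, dividing by the relative efficiency 3/pi = 0.955: 53 / 0.955 = 55.5, so 56 per arm, as stated.
- Dropout: 56 / 0.90 = 62.2, so 63 per arm; 63 x 3 = 189, as stated.

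The sample size reproduces. It concerns the primary outcome only and says nothing about precision for the long-term scores.

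**2. Recorded variables against their use in the analysis.**

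| Variable | Recorded (8.1) | Role in 8.4 |
|---|---|---|
| Gestational age | yes (also a stratum) | subgroup |
| Sex | yes (also a stratum) | none named |
| Birth weight | yes (birth measurements) | subgroup |
| Parents' education | yes | none |

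**3. Precision gain.** Let R2 be the share of score variance that the covariates explain within arms. It is not in the documents; 0.10 to 0.25 is assumed. The variance of an arm contrast is multiplied by 1 - R2, the interval width by sqrt(1 - R2), and the equivalent sample by 1/(1 - R2).

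| R2 | Variance factor | Width factor | Interval narrower by | Equivalent extra children |
|---|---|---|---|---|
| 0.10 | 0.90 | 0.949 | 5% | 11% |
| 0.25 | 0.75 | 0.866 | 13% | 33% |

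**4. What this means for power.** Noncentral t, one pairwise contrast, at the default level in 8.4.2 ("Unless otherwise specified, all statistical tests will be conducted at a two-sided significance level of 0.05"). The 20 per arm is an assumed size for a restricted subset such as K-WPPSI-IV. The 56 per arm is the planned number before the dropout allowance. R2 = 0.30 lies beyond the assumed range and is shown as an outer limit.

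| Per arm | Quantity | R2 = 0 | 0.10 | 0.20 | 0.30 |
|---|---|---|---|---|---|
| 20 | power for 0.5 SD | 34% | 37% | 41% | 45% |
| 20 | difference detectable at 80% power | 0.91 SD | 0.86 | 0.81 | 0.76 |
| 56 | power for 0.5 SD | 75% | 79% | 84% | 88% |

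**5. The cost of estimating the covariate effects.** Steps 3 and 4 ignore it. With f error degrees of freedom before adjustment and k covariate coefficients, the adjusted variance is raised on average by about (f - 1)/(f - k - 1). Take k = 4 (gestational age, sex, birth weight, parents' education, one coefficient each).

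- 60 children in three arms: f = 57, factor 56/52 = 1.077. Net variance is 0.90 x 1.077 = 0.969 to 0.75 x 1.077 = 0.808, so intervals are about 2-10% narrower.
- 168 children: f = 165, factor 164/160 = 1.025. Net variance is 0.923 to 0.769, so intervals are about 4-12% narrower.

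Stratification balances gestational age and sex, which makes this cost somewhat smaller. Coding education in several categories makes it somewhat larger.

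**The case against.** The case against is substantial on several points.

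- **The plan does not prescribe unadjusted ANOVA.** A reader might infer that it does. The two-way ANOVA has an unnamed second factor, which could be a stratification factor, and a multivariable line is present. This objection stands as a limit on the claim: the model is unspecified, which is not the same as stated to be unadjusted. It does not close the gap, because nothing points to birth size or parents' education, and logistic regression does not fit a continuous score.
- **Complete-case analysis is not stated.** A reader might infer it because no method for missing long-term scores is given. The documents are silent, and silence is not a rule.
- **Small numbers at every long-term visit are not shown.** Only K-WPPSI-IV is restricted by design. Every enrolled infant meets the Bayley-III and K-MBCDI indications, and K-DST, SDQ and BPFAS carry no such limit. No long-term attrition figure is given.
- **R2 is assumed, and one range is applied to quite different instruments.** This stands. In the K-WPPSI-IV group, selection on gestational age and birth weight narrows the spread of birth size, so R2 may be lower there.
- **Randomisation already protects the comparison.** This also stands. Omitting a predictor does not bias the contrast, and adjustment does not rescue an underpowered subset: 34% power becomes at most 45% in the example.

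**Conclusion.** The point holds as a modest, optional improvement to the secondary analyses. Section 8.4.2 names no covariate-adjusted model for the continuous long-term scores, although suitable baseline predictors are in hand. On the assumed R2 of 0.10-0.25, adjustment narrows intervals by about 5-13%, equivalent to 11-33% more children, before the small cost of estimating the covariate effects. Precision is scarcest for K-WPPSI-IV, but that cost is also largest there, and birth size may explain less.

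It would go too far to conclude that the planned comparisons are biased or invalid, or that adjustment would repair loss to follow-up. The documents give no attrition figure and no missing-data method from which to judge the latter. The primary outcome and its sample size are unaffected.

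**What to change.** In section 8.4.2, prespecify for each long-term score analysed as continuous a linear model (ANCOVA) with arm, the stratification factors gestational age and sex, birth weight, and parents' education. State how education is coded (which parent, which categories), keep the covariate set the same across instruments, and fix it before any long-term score is analysed. Report the adjusted arm contrasts with confidence intervals, and give the unadjusted comparison as a sensitivity analysis.

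If missing scores are imputed, do so as a supporting analysis and only among children for whom that test is indicated. K-WPPSI-IV scores should not be created for children outside its indication.

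The cost is a few lines of SAP text and a little more analysis work. Nothing further has to be collected.

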8.2 Clinical observation factors

8.2.1. Vital signs: SpO₂, blood pressure, heart rate, respiratory rate

8.2.2. Indicators for evaluating the patient's condition before feeding

(1) Behavioral organization states

State	Descriptor
1	Deep sleep
2	Light sleep
3	Drowsy or semi-dozing
4	Quiet alert
5	Active alert and aroused
6	Highly aroused, agitated, upset, and/or crying

2) Feeding readiness behaviors :

- ① Crying near scheduled feeding time
- ② Increased general activity level (involving increased heart rate)
- ③ Hand-to-mouth and sucking on hand
- ④ sucking pacifier

(If none of 1, 2, or 3 apply, provide a pacifier, and if sucking is present, check item 4.)

8.2.3. Indicators for evaluating oral feeding performance

Data will be collected through three evaluations:

- 1) The time point when oral feeding starts,
- 2) The time point when oral feeding volume reaches 50% of total feeding volume,
- 3) The time point when oral feeding volume reaches 100% of total feeding volume.

-Overall transfer (% volume taken/volume prescribed)

-Proficiency (% volume taken at 5 min/volume prescribed)

Protocol_DST and OSMS_oral feeding performance

- Rate of transfer (mL/min volume of milk consumed relative to the duration of the oral Feeding session)
- Volume loss (% volume of milk spilled from the lips as a percentage of the total milk transferred)

8.2.4. Neonatal Oral Motor Assessment Scale (NOMAS)

Evaluation time points:

- 1) Between 3-5 days after the start of oral feeding,
- 2) Within 3 days after the end of the intervention.

8.2.5. Korean Developmental Screening Test for Infants and Toddlers (K-DST), Strengths and Difficulties Questionnaire (SDQ), Behavioral Pediatric Feeding Assessment Scale (BPFAS)

Survey time point: 48 months of age \pm 3 months

Survey method: The survey will be conducted by implementing a web-based questionnaire, which will be sent via email or smartphone and returned through the same method.

8.3 Outcome

8.3.1. Primary outcome: The period from the start of oral feeding to the time when full oral feeding is achieved without any feeding-related side effects requiring special treatment.

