7.2 Randomization

In this study, eligible participants who meet all the inclusion criteria will be randomly assigned in a

Protocol_DST and OSMS_oral feeding performance

1:1:1 ratio to the control group, the DST group, or the DST + OSMS group. However, randomization will be stratified by gestational age and sex.

The randomization will be done using a block randomization method with block sizes of 3 and 6, generated through SAS 9.2. The randomization process will be managed via the MRCC website (<http://mrcc.snu.ac.kr>) using web-based randomization.

The detailed randomization procedure is as follows:

- Study coordinators will be provided with an ID and password for randomization.
- The study coordinators will log in to the MRCC website (<http://mrcc.snu.ac.kr>) and access the randomization screen.
- The study coordinator will enter the participant's basic information, test results, inclusion/exclusion criteria, and other relevant data, and click the confirmation button.
- If the participant is eligible, a randomization number will appear on the screen.
- The randomization screen will be printed, and one copy will be kept for records.
- The study coordinator will use the assigned randomization number to prescribe the corresponding intervention.

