7.3.4. Detailed method for each intervention

Both the experimental group and the control group will continue the use of non-nutritive sucking through a rubber nipple and oral support during feeding, which are currently standard practices in the neonatal intensive care unit.

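### The primary outcome depends partly on how fast staff offer oral feeds, and the plan does not say that those staff are kept from the allocation or that feeds offered are recorded

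*Combined protocol and SAP*

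**What the plan says.** Section 8.3.1 defines the primary outcome as "The period from the start of oral feeding to the time when full oral feeding is achieved", with the condition that no feeding-related side effect requires special treatment. Section 8.1 treats that milestone as the end of the intervention. Section 7.3.3 ties the end of the intervention to two consecutive days on which every feed is taken orally without special treatment.

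On allocation, the last step of section 7.2 reads: "The study coordinator will use the assigned randomization number to prescribe the corresponding intervention". The randomization screen is printed and a copy is kept. Nothing is said about who may see the order or the printout.

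On co-interventions, section 7.3.4 continues non-nutritive sucking and oral support in all arms, "which are currently standard practices in the neonatal intensive care unit". It does not mention the start or advancement of oral feeds.

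On masking, the paragraph headed 10.4.3.3 (within section 7) puts a screen in place for all interventions. Controls receive a 15-minute sham with the researcher's hand in the incubator. Section 7.3.2 gives the combined arm 15 minutes of DST plus 15 minutes of OSMS a day. The overview calls the trial blind in one row and open-label in another, and section 5 says open-label.

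On data, sections 8.1 and 8.2.3 record milestones (first oral feed, 50%, 100%) and feeding performance at those points. The number of oral feeds offered per day is not listed.

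**The concern.** An elapsed time to full oral feeding can shorten because infants feed better or because they are offered oral feeds sooner and more often. The overview states that DST is expected to help and that adding OSMS should help further. If staff who pace the feeds know the arm and share that expectation, the bias runs in the hypothesised direction and could be read as a treatment effect. If they pace trained infants more cautiously, a real effect could be hidden. Without a record of feeds offered, a difference in pacing between arms would be hard to see afterwards.

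**Working it through.** **1. What fixes the interval, and what does not.**

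| Element of SOF-FOF | What the protocol provides |
|---|---|
| Start (first oral feed) | Recorded as a milestone (8.1). No decision-maker, basis or masking stated |
| Pace between start and end | Milestones at 50% and 100% (8.1, 8.2.3). No decision-maker, basis or masking stated |
| End | Two-day tolerance criterion (7.3.3). No statement of who judges it or whether they are masked |

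Sections 7.3.1 to 7.3.3 govern the start, frequency and stopping of the study intervention, not feeding progression. The end is partly anchored; the start and the pace are not.

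**2. What the masking covers.** The screen and sham hide what is done at the bedside. They do not extend to the order in 7.2. Scheduled time also differs: the combined arm has 15 + 15 = 30 minutes a day against a 15-minute sham, so time behind the screen can reveal that arm. No passage names a blinded role.

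**3. The plan's own sample size (section 6.2).** Inputs: "Control group 20.8 days, DST group 14.6 days, and DST + OSMS group 10.0 days"; "The pooled standard deviation was calculated to be 7.19"; two-sided alpha 0.0167; power 80%; allocation 1:1:1. The smallest pairwise difference is 14.6 − 10.0 = 4.6 days.

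- Normal approximation: n = 2 × SD² × (z_alpha + z_beta)² / difference² = 2 × 7.19² × (2.393 + 0.842)² / 4.6² = 51.1, so 52 per group.
- Noncentral t: 53 per group.
- The t-test figure with the Mann-Whitney efficiency factor: 53 × π/3 = 55.5, so 56. This matches the plan. Section 8.4.2 lists Mann-Whitney, although 6.2 does not name the test used for sizing.
- Dropout: 56 / 0.9 = 62.2, so 63 per group; 63 × 3 = 189. This matches.

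The sample size is therefore not in question.

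**4. Sensitivity of the result to a pacing shift (two-sample t-test, 56 per group).**

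- Standard error of a difference: 7.19 × √(2/56) = 1.359 days.
- Critical t on 110 degrees of freedom at two-sided 0.0167: 2.430.
- Smallest significant difference: 2.430 × 1.359 = 3.30 days.

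With an assumed shift b, the test statistic follows a noncentral t with noncentrality b / 1.359 when there is no true effect. If b acts against the intervention and the true difference is 4.6 days, the noncentrality is (4.6 − b) / 1.359.

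| Assumed shift b (days) | Rejection rate, no true effect | Power for a true 4.6 days, shift against the intervention |
|---|---|---|
| 0 | 1.67% | 83% |
| 0.5 | 2.4% | 72% |
| 1 | 4.9% | 59% |
| 2 | 17% | 31% |
| 3 | 42% | 11% |

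The documents give no data on pacing, so b is an assumption throughout. The table shows sensitivity, not a predicted bias.

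**The case against.** The plan does make an effort at masking. A screen is used in every arm, controls have a sham, and the endpoint requires two days of tolerated full oral feeding, which limits how far faster offering alone can shorten the interval. The plan also measures skill directly: overall transfer, proficiency, rate of transfer and volume loss at three points (8.2.3), and NOMAS at two (8.2.4). A shorter SOF-FOF with no gain on these would itself point to pacing. All of this stands, and it limits the concern.

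Four stronger readings are tempting, and the documents do not support them.

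- A reader might infer that pacing is left to ward discretion. The protocol is silent, and the unit may have its own criteria.
- A reader might infer that the staff who pace feeds can read the arm in the orders. Section 7.2 does not say where the prescription is entered or who sees it. The defect is that access is not excluded.
- A reader might conclude that the trial could never separate skill from pacing. The skill measures give partial separation. What they lack is the number of feeds offered between milestones.
- A reader might size the bias by supposing 8 feeds a day, so 8 − 1 = 7 additions. One addition per 1, 1.5 or 2 days takes 7, 10.5 or 14 days, a gap of 3.5 to 7 days. The feed count and the paces are all assumed, and the plan tracks progress by volume. This is a scenario, not an estimate to set against the planned differences of 6.2 (20.8 − 14.6) and 4.6 days.

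A neutral order also cannot make the arms look identical, because session time differs.

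**Conclusion.** The concern holds as an avoidable route to bias in the primary outcome, not as evidence that bias will occur. The start and pace of the interval depend partly on staff decisions, no passage keeps the allocation from those who make them, and the masking described stops at the bedside procedure. A modest shift would matter: if pacing alone moved one arm by 1 or 2 days, the per-comparison false-positive rate would rise from 1.67% to about 5% or 17%. At half a day it would be 2.4%. These figures rest on 56 evaluable infants per group, SD 7.19, a t-test and an assumed shift. The change should be made; the sample size is unaffected.

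**What to change.** **(a) Section 7.2.** Enter the allocation on the ward as a neutrally worded study-session order. Keep the arm and the randomization printout only with the operators who deliver the sessions. State that staff who decide the start and advancement of oral feeds, and whoever judges the endpoint, have no access to either. Reconcile the blind and open-label labels in the overview, section 5 and the masking paragraph, naming who is masked, and acknowledge that session time may still reveal the combined arm.

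**(b) Section 8.1.** Record from the nursing chart the number of oral feeds offered each day from SOF to FOF, and report it by arm beside the primary result. This is useful even if masking fails, because it makes a difference in pacing visible.

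The clinical criteria for feeding remain for the unit, the same in all arms; none is proposed here.

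**Cost.** Order-set wording, a short protocol amendment and some data entry. Neither change adds a procedure for the infant or alters the sample size.
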